10.3 Statistical Analysis

The statistical test will be ANCOVA, probably MIXED MODEL in SPSS, or similar, for repeated measurements with main outcome group differences in the interaction of time and treatment allocation. *Ho hypothesis will be no*

difference between the treatments. Level of statistical significance will be $\alpha<0.05$ and $1-\beta=0.8$. These principles will be utilized in both stage one of the study and the main study.

Primary efficacy variable is troponin I. Intention to treat analyses will be performed and group differences in side effects will be analyzed and presented regardless of rejection of the H_0 hypothesis or not. All data will be entered and locked in the database, and treatment allocation information will not be revealed until complete dataset are obtained in the main study.

All adverse events, whether spontaneously reported by the patients or observed by the investigator, will be described and categorized both by their nature and severity using the NCI Common Terminology Criteria for Adverse Events, Version 4.03. An attempt to relate the incidence and severity of adverse symptoms to certain patient characteristics will be made.

11 STUDY MANAGEMENT

11.1 Investigator Delegation Procedure

The principal investigator is responsible for making and updating a "delegation of tasks" listing all the involved co-workers and their role in the project. He will ensure that appropriate training relevant to the study is given to all of these staff, and that any new information of relevance to the performance of this study is forwarded to the staff involved.

11.2 Study Amendments

If it is necessary for the study protocol to be amended, the amendment and/or a new version of the study protocol (Amended Protocol) will be notified to and approved by the Norwegian Medicines Agency and the Ethics Committee according to EU and national regulations.

11.3 Audit and Inspections

Authorized representatives of a regulatory authority and Ethics Committee may visit the centre to perform inspections, including source data verification. Likewise, the representatives from monitor may visit the center to perform an audit. The purpose of an audit or inspection is to systematically and independently examine all study-related activities and documents to determine whether these activities were conducted, and data were recorded, analyzed, and accurately reported according to the protocol, Good Clinical Practice (ICH GCP), and any applicable regulatory requirements. The principal investigator will ensure that the inspectors and auditors will be provided with access to source data/documents.

12 Ethical and regulatory requirements

The study will be conducted in accordance with ethical principles that have their origin in the Declaration of Helsinki and are consistent with ICH/Good Clinical Practice and applicable regulatory requirements. Registration of patient data will be carried out in accordance with national personal data laws.

12.1 Ethics Committee Approval

The study protocol, including the patient information and ICF to be used, will be approved by the regional ethics committee before enrolment of any patients into the study.

The investigator is responsible for informing the ethics committee of any serious and unexpected adverse events and/or major amendments to the protocol as per national requirements.

12.2 Other Regulatory Approvals

The protocol will be submitted and approved by the applicable competent authorities before commencement of the study, including local representatives of Data Inspectorate, Norway ("Personvernansvarlig" at Oslo University Hospital) and Norwegian Medicines Agency. Data security will be handled according to the updated EU general data protection regulations (GDPR).

The protocol will also be registered in www.clinicaltrials.gov before inclusion of the first patient.

12.3 Informed Consent

The investigator will give the patients full and adequate verbal and written information about the nature, purpose, possible risk and benefit of the study. They will be informed as to the strict confidentiality of their patient data, but that their medical records may be reviewed for trial purposes by authorized individuals other than their treating physician.

It will be emphasized that the participation is voluntary and that the patient is allowed to refuse further participation in the protocol whenever she wants. This will not prejudice the patient's subsequent care. Documented informed consent will be obtained for all patients included in the study before they are registered in the study. This will be done in accordance with the national and local regulatory requirements. The investigator is responsible for obtaining signed informed consent (ICF).

A copy of the patient ICF will be given to the patients. The signed and dated ICF will be filed in the Investigator Site File binder. A separate note stating that the patient has been provided with oral and written information about the study and has signed the study ICF will be stored in the patient's electronic medical record at the hospital.

The information will be given to potential participants at least 24h prior to registration of consent followed by randomization.

1.0 INTRODUCTION

Adequate uterus contraction after delivery of the baby is necessary to avoid excessive bleeding. Prophylactic administration of an oxytocin receptor agonist is first line practice. Intravenous injection of oxytocin has been the standard procedure, but serious cardiovascular adverse events have been reported. Lowering the dose or administering the drug as a 5-minute infusion may increase safety.

Carbetocin, a synthetic oxytocin receptor agonist, has significantly longer half-life, and may reduce blood loss compared with oxytocin. The hemodynamic vasodilatory effects are comparable to oxytocin(1), but potential differences in adverse effects on myocardium are not well described yet.

Carbetocin has been in clinical use in EU since 2007, and the efficacy is documented in several RCTs. In the proposed study, carbetocin will be used within then conditions of the marketing authorization. Oxytocin is the first line treatment and prophylaxis in Norway and most countries in the world.

According to recently published guidelines from EU drug authorities (EMA), oxytocin should be given as a slow 5-minute infusion in order to avoid hypotension. This has so far not been implemented in Norway. The pre-clinical and clinical experience of the two drugs are summarized in the Summaries of Product Characteristics.

Pregnancy and delivery is a natural process, but for many women this period is stressful and not without risks of morbidity, and even mortality. Circulatory adverse events leading to death have been reported after intravenous injection of oxytocin(2). Some studies indicate that oxytocin may lead to dose dependant ischemic ECG changes(3, 4), prolongation of QT time and liberation of biomarkers of myocardial cell death(3).

Previously we have demonstrated comparable vasodilatory effects of oxytocin and carbetocin(1). There is no clinical study comparing the specific myocardial effects of oxytocin with carbetocin. It may have great impact on the choice of standard medication if the cardiotoxicity of carbetocin is lower compared with oxytocin. The study of potential cardiotoxicity has to be performed in healthy women. Knowing that millions of labouring women have had uneventful injections of oxytocin and carbetocin after delivery, there is probably no reason to fear long lasting negative effects of either drug. Improved knowledge about the effects of the two drugs on heart and circulation will aid treatment decisions especially for women with underlying heart disease or hypertensive complications of pregnancy, but even for healthy women undergoing caesarean delivery.

The aim of the pilot study is to compare 0h (before C-section), 4h, 10h and 24h plasma concentrations of troponin I (highly sensitive methods), troponin T, NT-proBNP, CK-MB and other relevant myocardial markers and ECG changes in elective healthy C-section patients randomized to oxytocin 2.5 U or carbetocin 100 µg, by 1-minute injection immediately after delivery.

Based on the results from the pilot trial, sample size calculation for the main trial (CMT2) will be performed to answer which of the drugs causes more release of high sensitive troponin I.

Some clinical studies indicate that administering carbetocin will influence pain perception. One clinical study comparing carbetocin and oxytocin for prevention of PPH after caesarean

delivery, reported significantly reduced pain intensity in patients receiving carbetocin(5). A secondary analysis of postoperative opioid consumption in another clinical trial comparing hemodynamic effects of oxytocin and carbetocin, found a tendency of lower consumption of opioids in the carbetocin group, but the differences were not statistically significant(6). The CMT-pain trial, a substudy of the CMT trial, will be conducted to investigate group differences in reported pain intensity and opioid consumption. Information on the patients level of anxiety, depression and pain catastrophizing traits will be obtained prior to the operation. In addition, biobank material will be analysed for levels of inflammatory markers related to pain.

2.0 DATA SOURCE

2.1 Patients

We will conduct a double blinded randomized controlled trial where healthy women undergoing C-section will receive either oxytocin or carbetocin immediately after delivery of the baby. Ratio between the groups will be 1:1.

2.1.1 CMT pilot trial

Forty patients will be recruited from the general population of the birth clinics of Oslo University Hospital (OUH). Based on blinded analysis in this pilot trial, statistical power analysis and group size estimation will be performed to prepare for a larger confirmatory main trial (CMT2).

2.1.2 CMT2 trial

240 patients will be included into the CMT2 trial from the general population of the birth clinics of OUH and Akershus University Hospital (AHUS).

2.1.3 CMT pain trial

This trial will include 40 patients from the pilot trial and the first 40 patients from the CMT2-trial included at the birth clinic of OUH, Rikshospitalet.

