5.5 Concomitant Medication

In case of uterus atony, patients will be treated with oxytocin 1 U every 2 minute up to maximum 5 U. Any additional treatment of uterus, medical or surgical, will be decided by the attending obstetrician and anesthesiologist according to departmental procedures. Spinal anesthesia will be given according to departmental procedure, hypotension prophylaxis (phenylephrine 0.1 mg/ml) and intravenous volume (normal saline 10 ml/kg starting concomitantly with spinal anesthesia (see 6.2.2 for details). Pain intensity and opioid consumption will be registered for the patients included at Rikshospitalet, OUH, only. For these patients (Rikshospitalet, OUH) pain treatment protocol includes oral paracetamol 1 g and ibuprofen 400 mg 4 times pr day and IV morphine administered according to departmental procedure using a patient controlled analgesia pump (PCA). All interventions, including all administered medication will be registered with doses and timing.

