6.1 Flow Chart

[figure not shown]

Table 1. Trial flow chart

	Screening Period	Treatment Period	Treatment Period	Treatment Period			End of study		
Time	Within 14 days of treatment	Within 2 h of treatment	Time 0 (before C-section)	Time after C-section – 0 - 30 min	Time 4h	Time 6-10h	Time 24h	Time 48h	Time 48h
Informed consent	X	X							
Inclusion/exclusion Evaluation	X								
Medical History	X								
Demographics ¹⁾			X						
Vital signs ²⁾		X	X						
Blood samples ³⁾		X					X		
IMP administration			X						
Uterine tone				2.5 and 5 min					
Adverse event, pain intensity (only for patients at RH, OUH)			X	X	X		X	X	X
Record of concomitant medication			X		X				

1. Demographics including pre-pregnant weight, actual weight, height, age, gestational weeks, parity at baseline.
2. Blood pressure, heart rate, ECG, at baseline and until 30 min.
3. Hb, Na, Troponin I.

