6.2 By Visit

6.2.1 Before Treatment Starts

Potentially eligible participants will be screened by the principal investigator for inclusion at their last midwife consultation before their scheduled delivery. At Rikshospitalet, OUH, an additional screening of psychological distress and pain catastrophizing will be administered by self-report during the visit in order to assess a potential association with adverse events (post-surgical pain). Oral and written information will be given to each woman at least 24 h before her delivery and written informed consent obtained before randomization. Consent (ICF), participation and redrawing of consent will be documented in electronic patient journal (see 9.2). Name of trial, eligibility, date of signed consent and randomization number will be documented. Screened, but not consented patients will be registered by number. Screened but not included due to exclusion criteria or unfulfillment of inclusion criteria will be registered by number and reason for non-inclusion/exclusion.

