3.4.3 CMT pain trial

40 patients from the pilot trial and the first 40 patients from the CMT2 trial included at OUH, Rikshospitalet will be included in the trial.

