6.2.6 Postoperative pain and side effects

Pain at rest, pain after coughing, nausea and tiredness will be registered at 4h, 10h, 24h and 48 h after administration of test drug in the CMT pilot trial..

A numeric rating scale ranging from 0-10 is used (0 = no discomfort, 10 = maximal discomfort imaginable). The variables will be treated as continuous in the statistical analyses.

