6.2.8 QOL forms detecting level of anxiety, depression and pain catastrophizing trait

Prior to the operation the patients will be asked to fill in QOL forms detecting level of anxiety, depression and pain catastrophizing trait. Only in the CMT pain trial.

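### The SAP limits the pain trial to the first 40 CMT2 women at Rikshospitalet without giving a reason, while the protocol records the same data there with no limit; the possible cost is precision

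*SAP*

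**What the plan says.** **Population.** SAP 2.1.3 sets the pain trial as "40 patients from the pilot trial and the first 40 patients from the CMT2-trial included at the birth clinic of OUH, Rikshospitalet", and SAP 3.4.3 repeats it. Neither section explains the second 40. SAP 4.1.3 gives this trial its own primary endpoint, opioid consumption and pain intensity over 48 hours. SAP 7.1 has sample-size sections for the pilot and CMT2 but none for the pain trial.

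**Recording in the protocol.** The restriction is by site, not by number. Section 5.5 states: "Pain intensity and opioid consumption will be registered for the patients included at Rikshospitalet, OUH, only". The flow chart in 6.1 puts the same site restriction on pain intensity. For the questionnaires, section 6.2.1 states: "At Rikshospitalet, OUH, an additional screening of psychological distress and pain catastrophizing will be administered by self-report during the visit".

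**Recording in the SAP.** The scope varies by section. In 6.2.6, postoperative pain scores "will be registered at 4h, 10h, 24h and 48 h after administration of test drug in the CMT pilot trial". Section 6.2.7 defines morphine consumption for the pain trial. Section 6.2.8 restricts the questionnaires: "Only in the CMT pain trial". Section 2.3 lists pain, analgesics and the questionnaires with no restriction.

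**Models.** SAP 7.4.2 regresses the follow-up value on treatment and baseline. SAP 7.4.3 uses a Welch t-test for outcomes measured once, with median regression if the data are skewed. Neither includes a term for pilot versus CMT2.

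**The concern.** Under the protocol, the 41st CMT2 woman at Rikshospitalet is randomised, treated and followed for pain in the same way as the 40th. Under the SAP she is outside the pain trial. With no sample-size argument for the cut, the plan may leave out of the pain trial's primary analysis women whose data it intends to record anyway.

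Because the SAP's own definitions are narrower than the protocol's, a reader cannot tell which of four things happens to that woman's data: they are never recorded, they enter the pain trial, they are analysed only as a CMT2 secondary outcome, or they go unused. SAP 6.2.6 does not even cover pain scores for the 40 CMT2 women whom the pain trial needs.

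The pooled set also combines two successive randomised phases. Any difference in pain or opioid use between phases stays in the residual variance unless the model contains phase.

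**Working it through.** **The plan's own sample size.** The only calculated figure is 178 for CMT2 (SAP 7.1.2): SDs 0.79 and 4.48, difference 1.37, two-sided 5%, 80% power, unequal variances. At 89 per group:

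- SE = sqrt((0.79² + 4.48²)/89) = sqrt(20.69/89) = 0.482
- non-centrality = 1.37/0.482 = 2.84, with about 93 Satterthwaite degrees of freedom
- power = 80.3%, and 89 is the smallest group size that reaches 80%

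So 178 reproduces. It concerns troponin and does not support the 80 of the pain trial.

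**Inputs for the pain trial.** 40 pilot women and 40 CMT2 women (SAP 2.1.3), 1:1 allocation (SAP 2.1), two-sided 5% (SAP 4.2). The 80% power is borrowed from CMT2. The number n of CMT2 women at Rikshospitalet is not given; SAP 2.1.2 says only that 240 come from OUH and Akershus together. It is therefore an assumption, varied below from the cap upwards.

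**Formulas**, for a two-group comparison of one continuous outcome, with N = 40 + n:

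- detectable difference in SD units = (1.960 + 0.842) × sqrt(2/(N/2))
- SE relative to the SAP's 80 women = sqrt(80/N)

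For N = 80: 2.802 × sqrt(2/40) = 2.802 × 0.2236 = 0.63 SD.

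| n at site (assumed) | N | Detectable difference (SD) | Power at 0.5 SD | SE versus N = 80 | CMT2 women beyond the first 40 |
|---|---|---|---|---|---|
| 40 | 80 | 0.63 | 60.9% | no change | 0 |
| 60 | 100 | 0.56 | 70.5% | 11% lower | 20 |
| 80 | 120 | 0.51 | 78.2% | 18% lower | 40 |
| 120 | 160 | 0.44 | 88.5% | 29% lower | 80 |
| 160 | 200 | 0.40 | 94.2% | 37% lower | 120 |

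These are normal approximations; the t distribution gives 0.63 at N = 80 and 0.52 at N = 120. The 0.5 SD column is for illustration only, since the documents name no target difference for pain or morphine.

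**Is 80 reached?** SAP 2.1.3 counts women included. SAP 5.2 says some included women leave before receiving study drug, and it analyses only those treated. Eighty is therefore an upper limit on the analysed number.

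**Phase.** Allocation is 1:1 in both phases, so phase is close to balanced between arms. Leaving it out does not confound the comparison; including it removes between-phase variation.

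**The case against.** A reader might infer that the plan discards data already collected. The documents do not support that.

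- Both documents are plans and show no collected pain data from CMT2.
- SAP 6.2.6 to 6.2.8 tie the measures to the pilot or the pain trial. On that reading, women after the first 40 may have no such data to leave out.
- Postoperative pain and analgesic use are also secondary objectives (SAP 3.2), and SAP 7.4.1 analyses all secondary outcomes on the full analysis set. Later women's data could be used there, outside the pain trial's primary analysis.
- The number of women at the site is unknown. The wording about the first 40 suggests more than 40, but the loss cannot be counted and may be nil.

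A reader might also infer bias, or that 80 women are too few. Neither follows. A cut by enrolment order in a 1:1 randomised trial does not depend on outcome. With no clinically relevant difference or SD stated for pain or morphine, 0.63 SD cannot be called inadequate. The calculation is also for a single outcome, whereas pain is scored repeatedly. A fixed-size substudy that can report sooner is a legitimate choice.

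All of this stands, and it limits the point. It does not explain the cap, settle which women are measured, or give a reason to omit the phase term.

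**Conclusion.** The point holds as a disagreement between protocol and SAP on who has pain, opioid and questionnaire data, together with an unexplained cap on the pain trial. If the protocol's recording is followed and more than 40 CMT2 women are enrolled at Rikshospitalet, the primary pain analysis is less precise than those data would allow: between no loss (40 women) and a 29% reduction in SE forgone (120 women), on assumed numbers. If the SAP's narrower definitions govern, there may be nothing further to analyse, and what remains is the inconsistency. The missing phase term is a small and separate weakness in efficiency. None of this touches the troponin endpoint. It is a worthwhile improvement, not a serious flaw.

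**What to change.** 1. Reconcile the protocol (5.5, 6.1, 6.2.1) with the SAP (2.3, 6.2.6 to 6.2.8) so that both state which Rikshospitalet women have pain scores, opioid use and questionnaires recorded. Extend 6.2.6 at least to the CMT2 women in the pain trial.
2. In SAP 2.1.3 and 3.4.3, define the pain analysis set as the treated pilot women plus all treated CMT2 women at Rikshospitalet for whom the protocol already records these data, with no new collection. Keep the first-40 cohort as a sensitivity analysis. If the cap is retained instead, give its sample-size reason and say how later women's data will be analysed.
3. Add a pilot/CMT2 term to the pain-trial models. For total morphine, replace the plain two-sample t-test with regression on treatment and phase; the median-regression fallback can carry the same term.

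The cost is mainly SAP wording, with protocol wording only where the two must agree. The real downside is that the pain results wait until CMT2 recruitment at that site is complete. Protocol 10.3 already withholds treatment allocation until the main-study data are complete, so on that text the added delay may be small. The phase term costs one degree of freedom.

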2.2 Inclusion and exclusion criteria

Inclusion criteria are healthy pregnant women aged 18 to 50, singleton pregnancy at gestational age 36 weeks or more, who are able to read and understand Norwegian. Patients with placenta pathology, bleeding disorders, organ failure, prolonged QT-time or other serious cardiac diseases, epilepsy or known intolerance to any of the two drugs will be excluded from entering the trial.

2.3 Follow-up and timing of measurements

Patients will be followed for a period of 48 hours after the administration of study drug. In the pilot trial, blood samples will be drawn at 0h, before C-section (=baseline), and at 4h, 10h and 24h after delivery (=test drug administration). The myocardial biomarkers including high sensitive troponin I, troponin T, CK, CK-MB and NT-proBNP will be measured at all time points. If indicated by increase in some of the specific biomarkers, which will be analysed consecutively, an additional sample at 48h will be included.

During the C-section the patients will be attached to a Holter-monitor that will allow us to read ECG changes that are triggered by administration of test drug. The first ten minutes immediately following administration of study medicine will be evaluated for ST-segment changes, duration of ST-segment changes, prolonged QT-time and occurrence of arrhythmia. Data on ECG changes will be analysed only in the pilot trial.

In the CMT2 trial, blood samples of high sensitive troponin I and levels of sodium and hemoglobin will be measured at 0h and at an interval of 6-10h after study drug administration.

Data on uterine contraction, routine assessments of newborn status, side effects of test drug, consumption of analgesics and reported level of postoperative pain, nausea and tiredness will be obtained. Prior to the C-section patients will be asked to fill in standardized self-reporting forms designed to determine level of anxiety, depression and pain catastrophizing traits.

